3.2 EXCLUSION CRITERIA

Exclusion criteria will include: 1) any history of chronic medical or neurological disorder (e.g., traumatic brain injury, cardiovascular disease), 2) metal exposure, pacemaker, claustrophobia, cochlear implant, or colorblindness 3) current illness or infection, and 4) any condition that would prohibit them from engaging in a physical exercise testing session.

3.3 RECRUITMENT

We plan to recruit participants to test over a four-year period. This should provide ample time to recruit participants. It also allows us time to alter our recruitment efforts if we are not meeting targets. We will evaluate recruitment every two months to make sure we are on track to hit our targeted number of participants. Based on previous work by our laboratory and others in the area, we will use recruitment strategies that are effective within our community. Specifically, we will advertise for participants at Baylor University using the participant subject pool, on flyers across campus, through ads at local shops and stores, and on local social media sites.

3.4 CONSENT

Written consent form: Participants will be emailed a consent form and asked to read it before coming into the laboratory (see participant consent form). The purpose of sending the consent form prior to the study is to ensure participants have a proper amount of time to consider their participation and consent. The email will also include information about what the participant should do to be prepared for the visit: no vigorous exercise or alcohol within 12 hours of participating in the study, no caffeine, food, or drink within 2 hours of the study (water is ok), and no current illness (e.g., strep throat). Participants will also be asked to wear comfortable, loose fitting clothes that they can exercise in (to aid in ease of putting on blood pressure cuff and electrodes and for exercising).

At the beginning of their first scheduled visit, participants will be presented with the consent form again and the experimenter will walk the participant through the consent form and the protocol of the study (i.e., explain what will happen during the study). The experimenter will also go over all risks associated with the study and ensure that the participant understands the risks. During this period, the participant will be encouraged to ask the experimenter any questions. The participant will then be asked to sign the consent form indicating that they understand the details of the study and consent to participating in the study before they can participate in the actual study.

The protocol will be the same for all participants (i.e., there will be no randomization). Participants have the right to withdrawal at any point during the study. They will be notified that they will receive their \$50 at the completion of the neuroimaging portion of the laboratory.

4.0 RESEARCH DESIGN, METHODS, AND STUDY ACTIVITIES

Rationale: Previous research has identified areas of the brain associated with psychological stress and cardiovascular responses to stress; however, this research has not examined what is thought to be the most detrimental responses to stress, known as metabolically exaggerated²⁸. Participants will have their metabolic and cardiovascular responses to stress measured, as well as undergo an fMRI scan to examine their stressor-evoked neural responses. The hypothesis here is that a multivariate pattern of stressor-evoked responses will be able to predict the magnitude to which cardiovascular responses to stress are excessive of metabolic demand and that this pattern will encompass areas implicated in stress processing and cardiovascular control. This aim will be vital in elucidating the neurophysiological pathways of metabolically excessive cardiovascular responses to stress by identifying key brain areas that are related to the peripheral responses.

Design: The protocol will be the same for all participants.

Duration: Visit 1 will take approximately 2 hours and Visit 2 will take approximately 2 hours. The total commitment will be 4 hours.

Visit 1 Protocol: Visit 1 is designed to determine the additional heart rate (i.e., degree to which each participant's response to stress is metabolically inappropriate). Participants will come to the laboratory to engage in a standard stress testing paradigm. Following instrumentation with cardiovascular equipment and body metabolic measuring equipment, participants will be given 20 minutes to adapt to the laboratory environment. This will be followed by a 10-minute formal resting baseline, and 18-minutes of acute psychological stress tasks (MSIT and Stroop task), see description below⁹. This will then be followed by four 4-minute bouts of cycling exercise incrementally increasing in demand¹⁴ and will include with a maximal exercise test (described below). Participants will fill out questionnaires regarding demographics and health behaviors.

Visit 1 Measurements: Cardiovascular activity will be measured continuously⁴³ throughout the protocol using electrocardiogram and will be calculated for each minute of the protocol using Mindware Kubios processing software³⁴. Body metabolic rate, indexed by oxygen consumption, will be measured on a breath-by-breath basis assessing ventilation and analyzing inspired and expired gas composition using an integrated system. Metabolic rate will then be averaged for each minute. Additional heart rate will be calculated by first computing individual regressions of oxygen consumption on heart rate using data from rest and each of the 4-minute bouts of the graded exercise test¹⁴. The computed regressions for each participant will then be used, with each individual's observed oxygen consumption recorded during stress, to "predict" what heart rate should be during baseline and during the MSIT (acute psychological stress). The difference between observed heart rate and predicted heart rate will be additional heart rate, which represents heart rate in excess of body metabolic demand.

Visit 2 Protocol: Visit 2 is designed to measure stressor-evoked neural activity, required to develop multivariate analyses to predict metabolically excessive responses (i.e., additional heart rate). The same 150 participants will come to the VINS 17 CoE to engage in a functional magnetic resonance imaging protocol. The protocol will consist of a structural scan, followed by a functional scan during which participants will engage in the MSIT and Stroop.

Visit 2 Measurements: Functional and structural images will be obtained on a Philips Ingenia 3.0 Tesla Omega MRI scanner equipped with a 32-channel head coil. Blood-oxygen level-dependent (BOLD) images will be acquired over the stressor

[figure not shown]
period with the following parameters: FOV = 205 x 205 mm², matrix size = 64 x 64 mm², TR = 2,000 ms, TE = 28 ms, and FA = 90°. Functional scans will be obtained at rest and during an acute psychological stress task (MSIT).

Acute psychological stress tests: The MSIT is composed of two conditions: a congruent, control, condition and an incongruent, stress-inducing condition^{9,42,45}. Participants are asked to identify the number that is different from two other numbers in a visual display by pressing 1 of three buttons on the response glove. Each finger corresponds to a specific number (1 = index finger, 2 = middle finger, 3 = ring finger). For the control, congruent conditions the number appears in a location that is aligned with the respective finger position. For the incongruent (stress) condition the correct number appears in a position that is not aligned with the answer (see Figure 4). To increase stressfulness, the task includes elements of time pressure and social evaluation⁹. The test has been shown to be comparable to other standard psychological stress tests⁹, has good test-retest reliability³², and reliably perturb the physiological system^{9,38,32}. I have recently demonstrated through pilot testing that participants can engage in the MSIT while having metabolic activity measured and that there is strong test-retest reliability for measuring metabolically excessive heart rate responses to the MSIT. The Stroop interference test is similar to the MSIT, but colors are used instead of numbers³⁸. Both tasks have been used extensively in research³⁸.

Procedures and Activities for First Laboratory Visit:

- Experimenters will greet participants as they enter the lab and lead them to the lab waiting room.
- Once in the lab waiting room, participants will be given a copy of the consent form. The experimenter will walk the participant through the consent form and clearly explain all risks associated with the study. The participant will have the opportunity to ask any questions during and after the explanation (i.e., before signing the consent form). If the participant is still willing to participate in the study, he/she will sign the consent form.
- The experimenter will then set up the physiological equipment to measure blood pressure throughout the protocol. Participants will be asked to sit quietly for 10 minutes to adapt to the position of sitting. Blood pressure will be measured every 2 minutes on the non-dominant arm using a standard brachial artery cuff and a semi-automated sphygmomanometer for a total of 10 minutes. Before placing the blood pressure cuff on the arm of the participant, participants will be given the opportunity to ask any questions about the equipment. Participants will then be told the blood pressure cuff is similar to the one used at doctor's offices, with the exception that it will inflate with the push of a button (rather than someone pumping). Participants will be asked to sit quietly and the experimenter will inflate the blood pressure cuff once to ensure the participant is comfortable with the positioning and tightness of the cuff.
- The experimenter will then set up the physiological equipment to measure heart rate throughout the protocol. Electrocardiogram (ECG) will be recorded to determine heart rate. Three electrodes (circular stickers with a place in the center to attach wires) will be placed on the participants. Two electrodes will go just below the collar one and one electrode will go on the last rib on the left side. Participants will have the option to place the electrodes on themselves or have a researcher assist them. Three wires (one to each electrode) will then be attached and participants will be given a small box to clip on their pants (MindWare Mobile Impedance Cardiograph, Model 50-2303-00). The ECG data will be transmitted to a computer in which the trace of heart rate activity will be recorded. All data transmitted is de-identified.
- Participants will then be fitted with the face mask and hooked up to the Parvo Medics system to begin measures of their metabolic system. Oxygen consumption measured using an automated gas analysis metabolic system (Parvo Medics TrueMax 2400, Salt Lake City, UT) during a graded exercise test (standard Bruce protocol) on a treadmill (Spirit Medical MT200, Jonesboro, AR). Prior to each test, the gas analyzers will be calibrated with standard gases (O₂ and CO₂) of known concentrations.
- Once comfortable with the equipment set-up. Participants will begin the acute psychological stress and exercise paradigm. Below is a table outlining the paradigm.
- During the baseline periods, participants will be asked to sit quietly.

Figure 4. Schematic of the MSIT task and response options.
Participants identify the number that is different, not the position.

- The stress task will be the MSIT and Stroop (described above).
- The exercise portion will consist of a graded exercise test on a stationary bike (Monark, Sweden). Each exercise stage will be 4-minutes in duration and the participants will be requested to maintain a pedal rate of 50 revolutions per minute throughout the test. For the first 4 minutes, there will be no friction load on the wheel, but for each subsequent exercise stage, increasing friction loads will be applied to yield exercise power demands of 30, 60, and 90 W, respectively¹⁴. All participants will be requested to complete these initial four exercise stages. After the fourth stage, friction load will continue to increase in 30 W increments every 4 minutes until the participant reaches volitional exhaustion. Ratings of perceived exertion (RPE) (6-20 point Borg category RPE scale)⁴⁶ will be measured at the end of each 4 minute stage. Cardiovascular fitness will be determined from each participant's maximal oxygen consumption ($VO_{2\max}$) measured using an automated gas analysis metabolic system (Parvo Medics TrueMax 2400, Salt Lake City, UT) and a Hans Rudolph face mask during the exercise test. Prior to each test, the gas analyzers will be calibrated with standard gases (O_2 and CO_2) of known concentrations. Expired gases will be monitored throughout the test. $VO_{2\max}$ will be determined by averaging the 2 highest consecutive 20 sec oxygen (O_2) consumption readings recorded, which will be subsequently compared to age- and gender-specific normative values (American College of Sports Medicine, 2018). The test will be deemed to be maximal providing it satisfies 3 or more of the following criteria: leveling of oxygen consumption, respiratory exchange ratio (RER) > 1.1 , HR within 10 beats of the age predicted maximum and volitional exhaustion (RPE ≥ 17).
- After completing the exercise, participants will have the equipment removed and then have the opportunity to sit quietly until their heart rate goes back down to resting.
- Participants will then have anthropometric measurements taken:
 - Height and Weight: Total body weight (kg) and height (cm) will be determined on a standard dual beam balance scale and stadiometer (Detecto), respectively. Body weight will be recorded to the nearest 0.1 kg and height to the nearest 0.1 cm.
 - BMI: BMI will be determined from weight and height, where BMI equals weight (kg) / height (m^2). All BMI results will be recorded to the nearest 0.1 kg/ m^2 .
 - Waist circumference: Since waist circumference is positively correlated with abdominal fat content, this will be used as an adjunct marker of obesity for recruitment purposes. When standing at the participant's right side, a measuring tape will be extended parallel to the floor around the waist at the uppermost border of the right iliac crest. The measurement will be read to the nearest 0.1 cm at the end of the participant's normal expiration. A minimum of 2 measurements will be taken; however, if these vary by more than 2 mm a third measurement will be performed. Participants will also be given the option to place the tape measure around their own waist and hip for measurements if they would feel more comfortable. Every effort will be made to ensure male participants will have this measured by male RAs and female participants by female RAs. The participant is always given the option to take their own measurements with instructions from the RAs. There are always two RAs present during testing and the participant has the measurements taken in a private room (i.e., with two RAs and no other participants).
- Participants will also fill out questionnaires regarding demographics and health behaviors.

Procedures for the Second Laboratory Visit:

- Experimenters will greet participants as they enter the lab and lead them to the lab waiting room.
- Experimenters will walk the participants through the protocol of what will happen during the visit and give participants the opportunity to ask any questions they may not have asked during the first visit.
- Experimenters will then explain to participants the importance of removing any metal on their body and give them the opportunity to go into the changing room and remove any clothing with metal. Extra clothes without metal (basketball shorts and large t-shirts will be available if participants need them).
- Participants will then be walked into the scanning room and set-up for the scanning. The experimenter will ensure that the participant feels safe and comfortable in the scanning environment. If, for any reason, the participant appears to be becoming claustrophobic, they will be removed.
- Participants will be fitted with a blood pressure monitor and pulse oximeter to measure cardiovascular activity.
- Participants will engage in a 5 minute structural MRI scan, followed by functional scans during which they will engage in the MSIT (described above).
- After completion of the study, participants will be debriefed and have the opportunity to ask any questions.
- They will then be thanked for their time and provided with their payment.

Deception: The deception in the study has to do with the acute psychological stress task. Participants are told that they are being videotaped and that independent body language experts will review the videotape to analyze for signs of anxiety. However, the video camera is not actually recording during the task. Research suggests the addition of social evaluation in a laboratory stress paradigm makes the stress task more “life-like” and elicits a greater anxiety response⁴⁷. It is important to emphasize that although participants think they are being video recorded, they are not actually being video recorded and no body language expert will review the tape. The PI has used this deception in multiple studies at Baylor University. Participants will not be made aware of this deception until after the second laboratory visit due to the same deception taking place during both visits.

Debriefing: At the end of the study visit participants will receive debriefing. During the debriefing period, participants will be told that the video camera was not actually taping them and will be informed that this was meant to help evoke “stress” in the stress condition. If a participant is upset at the close of the debriefing, they will be referred to the counseling center and an incident report will be submitted. The debriefing sheet is included as a separate document in this application. Participants will also be provided with the PI’s information should they want to contact her regarding the deception.

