Autonomic responses to stress and future cardiovascular disease risk. There is longstanding and cumulative epidemiological evidence that individuals who exhibit a phenotype characterized by the expression of large-magnitude cardiovascular reactions are at elevated risk for clinical and preclinical endpoints of CVD⁵⁻⁸. My work and the work of others demonstrates that individual differences in these responses are relatively stable⁹⁻¹³. Moreover, cardiovascular responses during acute psychological stress, stress that does not require physical exertion, can be metabolically inappropriate—meaning that the cardiovascular system is working in excess of metabolic demand¹⁴⁻²⁴. To determine if cardiovascular responses are metabolically appropriate, we measure oxygen consumption (marker for metabolic activity) and cardiovascular activity at rest and during a graded exercise test. The cardiovascular and metabolic responses to moderate exercise is a marker for metabolically appropriate heart rate changes¹⁴. Individual regressions of oxygen consumption on heart rate are calculated based on measurements during exercise. The computed regressions for each participant are then used with their oxygen consumption scores recorded during stress to “predict” what their heart rate should be during baseline and acute psychological stress. The difference between observed heart rate and predicted heart rate is called additional heart rate, which represents heart rate in excess of metabolic demand (i.e., the degree to which the heart is responding inappropriately or in excess during psychological stress). Figure 2 displays a representation of predicted heart rate versus actual heart rate during a standard psychological stress testing paradigm¹⁴. The lack of physical exertion during psychological stress does not perturb the metabolic system, which results in predicted heart rate being the same as rest. However, participants, on average, demonstrate an increase in heart rate in excess of the metabolic demand. A longstanding view is that the repeated and cumulative expression of such metabolically-disproportionate, stressor-evoked, cardiovascular reactions contribute to, or exacerbate, pathophysiological changes that are conducive to CVD and CVD events among vulnerable individuals¹⁴⁻¹⁷. Recently, it has been proposed that the brain generates anticipatory visceromotor commands to alter cardiovascular physiology to prepare individuals to cope with psychological stressors²⁵ and that these commands are “visceral predictions”, insofar as to anticipate behavioral demands engendered by appraised stressors^{26,27}. Individuals with metabolically disproportionate responses may be displaying visceral prediction errors²⁸. The proposed work is both conceptual and empirical and provides a rationale for examining, in the context of CVD risk, the relationship between brain systems for visceral control and body metabolically exaggerated responses to stress.

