6.0 STATISTICAL ANALYSIS

All participants will receive a unique ID for the study. IDs will be given starting with the number 9000. Questionnaire data will be collected through the Qualtrics survey system using tablets in the laboratory. Qualtrics will store the data on an encrypted server that will only be accessed by the Co-Investigator, primary RA, and students working on the study.

Analytic plan: Averages of the main study variables will be calculated for the main analyses of examining cardiovascular, metabolic, and neural activity at rest and during the acute psychological stress task. Reactivity will be calculated as: Stress activity – Baseline activity. fMRI data will be preprocessed and analyzed with statistical parametric mapping software (SPM12; <http://www.fil.ion.ucl.ac.uk/spm>) using established realignment, co-registration, smoothing, and motion correction analyses³⁸. Stressor-evoked brain activation will be determined by comparing the BOLD signal activity during the incongruent (stress) versus congruent (control) condition^{9,38}. For the analyses between stressor-evoked cardiovascular activity and stressor-evoked neural activity, machine learning techniques will be used to generate a multivariate pattern (3D regression weight map) that relates to heart rate and metabolic responses to stress. The study will then test if this generated multivariate pattern can reliably predict cardiovascular and metabolic responses to stress. Recent papers examining brain multivariate pattern prediction of cardiovascular responses to stress found the between subjects correlations to be relatively small, $r = \sim .20$. Based on these results, with alpha set at .05 and power = .80, it is estimated we will need a sample of at least $N = 140$.

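### Baseline and stress heart rate are both predicted from stress-period oxygen consumption, and Section 6.0 does not name the additional heart rate score to be analysed

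*Combined protocol and SAP*

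**What the plan says.** Additional heart rate is observed heart rate minus the heart rate predicted from oxygen consumption by a regression fitted to each participant.

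- **Prediction step.** Section 4.0 (Visit 1 Measurements) uses the participant's "observed oxygen consumption recorded during stress, to 'predict' what heart rate should be during baseline and during the MSIT". Section 1.0 gives the same rule, for the resting period as well as the stress period: "The computed regressions for each participant are then used with their oxygen consumption scores recorded during stress". Neither section says that baseline oxygen is used for the baseline prediction.
- **Expected result.** Section 1.0 says that psychological stress does not perturb metabolism, "which results in predicted heart rate being the same as rest".
- **Calibration data.** Section 1.0: "Individual regressions of oxygen consumption on heart rate are calculated based on measurements during exercise". Section 4.0: "individual regressions of oxygen consumption on heart rate using data from rest and each of the 4-minute bouts of the graded exercise test".
- **Target of the brain pattern.** Section 4.0 (Visit 2 Protocol) describes the neural data as "required to develop multivariate analyses to predict metabolically excessive responses (i.e., additional heart rate".
- **Analysis section.** Section 6.0 defines reactivity as the stress value minus the baseline value, without saying for which variables. It describes the outcome as a "multivariate pattern (3D regression weight map) that relates to heart rate and metabolic responses to stress". Additional heart rate does not appear there.

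**The concern.** The only oxygen input named is the one recorded during stress, and it serves two periods. Read literally, the baseline prediction uses oxygen from the wrong period. The Section 1.0 remark that predicted heart rate stays at its resting value then becomes true by construction. It carries information only if each period's own oxygen is used.

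The gap in Section 6.0 adds to this. Additional heart rate could be analysed as a stress-period level or as a change from baseline, and the plan does not say which. If it is taken as a change under the literal rule, the metabolic correction drops out. The outcome is then ordinary heart rate reactivity. Section 1.0 says previous work examined only ordinary cardiovascular reactivity and presents the step beyond it as the study's novelty. At stake is whether the analysed score measures heart rate in excess of metabolic demand.

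**Working it through.** The documents give no numerical value for this score, so there is no figure to reproduce. The check is algebra, followed by illustrations on assumed values.

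**Notation.** H is observed heart rate, V is oxygen consumption, and P(V) is the heart rate predicted from V with slope B. Subscripts b and s mark baseline and stress.

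**Score as written**
- Baseline: H_b − P(V_s)
- Stress: H_s − P(V_s)
- Change: [H_s − P(V_s)] − [H_b − P(V_s)] = H_s − H_b, which is raw heart rate reactivity

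**Score with own-period oxygen**
- Baseline: H_b − P(V_b)
- Stress: H_s − P(V_s), the same as above
- Change: (H_s − H_b) − B × (V_s − V_b)

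The two versions therefore differ by B × (V_s − V_b) in the baseline value and in the change, and not at all in the stress-period level.

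**Size (slopes and oxygen differences are assumed)**

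| Slope, bpm per L/min | Difference 0 | 0.02 L/min | 0.05 L/min |
|---|---|---|---|
| 40 | 0 | 0.80 bpm | 2.0 bpm |
| 48 | 0 | 0.96 bpm | 2.4 bpm |
| 60 | 0 | 1.20 bpm | 3.0 bpm |

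Example: heart rate 70 at rest (on the fitted line) and 82 under stress, slope 40, difference 0.05. The stress level is 82 − (70 + 2) = 10 under either rule. As written, the baseline value is 70 − 72 = −2 and the change is 10 − (−2) = 12, the raw reactivity. With own-period oxygen the baseline value is 0 and the change is 10.

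**Does the literal rule track the true score less well?** This was simulated with 200,000 participants per scenario, all inputs assumed:
- calibration at 0.30, 0.60, 0.90, 1.20 and 1.50 L/min
- rest heart rate 72 (SD 9) and slope 48 (SD 8)
- mean stress oxygen 0.32 L/min
- true additional heart rate 10 (SD 5) under stress and 0 at baseline
- a relation that is linear from rest through exercise

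With no person-level spread in stress oxygen, baseline additional heart rate averaged −1.0 to −1.6 bpm as written, against 0.0 to −0.9 with own-period oxygen. The change averaged 10.9 to 11.0 against 10.0 to 10.3. With mean stress oxygen at 0.35 (a difference of 0.05) the change averaged 12.4 against 10.0 to 10.3.

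Correlation with the true score, as-written change v own-period change, by person-level SD of stress oxygen (L/min):

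| Measurement error (SD) | SD 0 | SD 0.03 | SD 0.06 | SD 0.10 |
|---|---|---|---|---|
| Heart rate 3 bpm | .76 v .77 | .74 v .76 | .70 v .77 | .61 v .76 |
| Heart rate 5 bpm | .58 v .58 | .57 v .58 | .55 v .58 | .50 v .58 |
| Oxygen 0.06 L/min | 1.00 v .78 | .96 v .78 | .86 v .77 | .72 v .78 |
| Oxygen 0.10 L/min | 1.00 v .59 | .96 v .60 | .86 v .60 | .72 v .60 |
| Both, 4 bpm and 0.06 L/min | .66 v .59 | .65 v .59 | .62 v .58 | .56 v .58 |

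When stress oxygen is near rest in everyone, the as-written change is within .01 of the own-period change or better. It is lower in two of five scenarios at SD 0.06 and in four of five only at SD 0.10.

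**The case against.** The strongest reply is that this is a drafting slip with little consequence. Section 1.0 compares predicted heart rate between periods, which makes sense only with own-period oxygen, and resting oxygen is collected. Figure 2 and the cited source for the method, neither of which can be seen here, may make the intended computation plain. The stress-period level, arguably the natural reading of the target in Section 4.0, is the same under either rule. The cancellation needs two steps: following the oxygen wording literally, and applying Section 6.0's general reactivity rule to a score that section does not mention. All of this stands, and it limits the point. It does not remove it, because the rule is written the same way in two sections and nothing elsewhere corrects it.

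A reader might go further and infer any of the following. The documents do not support them.

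- **That the study will analyse raw reactivity.** Section 6.0 does not say that its rule applies to additional heart rate.
- **That the study loses power or accuracy.** An error of the same size in everyone leaves a between-person correlation unchanged. The as-written change is mostly worse only at an assumed SD of 0.10 L/min. That is five times the assumed mean rise of 0.02 and puts about 42% of participants below resting oxygen during stress (normal probability below −0.02/0.10 = −0.2). The documents give no figure for this spread.
- **That the regression wording spoils the score.** Oxygen regressed on heart rate is the reverse of the stated use, but this is probably loose wording. In the simulation an inverted fit multiplies the level's correlation with the true score by .97 to 1.00. The Section 1.0 description of the calibration as exercise data conflicts with Section 4.0, but Section 4.0 is the methods text and includes rest. Both are secondary wording points.

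**Conclusion.** The prediction rule is wrong as written, and it should be corrected. Under it the baseline and stress predictions are identical, and baseline additional heart rate is in error by slope × (stress minus baseline oxygen). That is 0 to 3 bpm over the assumed ranges, and nil if stress oxygen equals rest. The identity and the cancellation are exact; the bpm figures rest on assumed slopes and oxygen differences.

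Section 6.0 separately leaves the outcome of the brain pattern unnamed and its form, level or change, undecided. The two faults matter most together, because they permit an analysis that follows the text and contains no metabolic correction. The damage is to the meaning and reproducibility of the score. Own-period oxygen is probably what is intended, so the point concerns the written plan and is not evidence that the score has been miscalculated.

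**What to change.** In Sections 1.0 and 4.0, state the computation once and identically, for example: *For each participant, heart rate (response) is regressed on oxygen consumption (predictor) using rest and the four 4-minute exercise bouts. Baseline heart rate is predicted from baseline oxygen and MSIT heart rate from MSIT oxygen. Additional heart rate is observed minus predicted within each period.* The calibration data are those Section 4.0 already specifies; this wording also settles the regression direction and the conflict with Section 1.0.

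In Section 6.0, name additional heart rate as the outcome of the brain pattern. Say, before the pattern is trained, whether it is the stress-period level or the change from baseline. Either is defensible.

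The cost is a few sentences and lines of code. No new data are needed, since rest oxygen is already collected for the calibration. The downside is that baseline oxygen measurement error now enters the baseline prediction and the change score. In the simulation with all error in oxygen and no person-level spread, the own-period change correlates .59 to .78 with the true score, against 1.00 for raw reactivity. Large oxygen error also flattens the fitted slope (mean level 9.4 against a true 10). Both are reasons to choose between level and change deliberately.
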